6.5 Study Termination

If the study sponsor or investigator discovers conditions arising during the study that indicate the study should be halted, the study must be terminated after appropriate consultation between the study sponsor, project manager, and investigator. Conditions that may warrant termination include, but are not limited to, the following – the discovery of an unexpected, significant, or unacceptable risk to the subjects enrolled in the study, insufficient adherence to protocol requirements.

7 DATA HANDLING AND RECORD KEEPING

7.1 Archiving Study Records

Essential documents should be retained on site for a minimum of 2 years after the last approval of a marketing application in an ICH region and until there are no pending or contemplated marketing applications in an ICH region or at least 2 years have elapsed since the formal discontinuation of clinical development of the investigational product. Once the 2 years have elapsed, essential documents will be transferred off site to a secure location and retained for up to 7 years. The documents will be retained for a longer period if required by the applicable legal and regulatory requirements.

7.2 Statistical Methods

7.2.1 General Statistical Methods

All data collected during the study will be presented in data listings. Summary tables and analyses will be based on the following analysis populations:

Safety population:	All enrolled subjects who received study treatment.
Intention-to-treat (ITT) population:	All enrolled subjects, regardless of whether they received study treatment.
Per protocol (PP) population:	All subjects in the ITT population for whom no major protocol violations occurred.

The primary population for analyses of efficacy data will be ITT population. A supportive analysis will be presented for the PP population if this is significantly different from the ITT population. The assessment of safety will be based on the safety population.

Continuous data will be summarized by treatment group using descriptive statistics (number, mean, median, standard deviation, minimum, and maximum). Categorical data will be summarized by treatment group using frequency tables (frequencies and percentages). Ninety-five percent confidence intervals will be constructed for proportions of successes.

Statistical tests will be used for analysis. The analysis will be 2-sided and conducted at the 0.05 significance level. An analysis of means using an independent samples t-test and ANOVA will be used. Primary analysis will be completed with the help of a chi-square analysis and assessment of relative risk and odds ratios.

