Study Design:	This is a double-blind, pilot study with 20 subjects to determine the tolerability and efficacy of topical AFX 5931 in the treatment of mild to moderate hand dermatitis. Subjects are screened up to 30 days before the baseline visit. Subjects who meet the eligibility criteria may qualify for the study. Subjects will be randomized in a 3:1 ratio to receive either the active or vehicle medication. 15 subjects will receive the active, therapeutic product and 5 subjects will receive the inactive, vehicle product. Subjects will complete 4 study visits according to the following 4-week timeline: Day [-30] – [-1] (Screening), Day 0 (Baseline), Day 14 (Follow-Up), Day 28 (Follow-up ET EOS). At Visit 2, IP will be dispensed and baseline readings of efficacy as well as safety/tolerability assessments will be obtained prior to application of the IP. Subjects will apply IP twice daily and compliance will be monitored by periodically reviewing the subject diary. The evaluations that will be used to measure efficacy of the product will be the Investigator's Global Assessment and Hand Eczema Severity Index. The Subject's Local Dermal Tolerability Assessment and Local Skin Reaction Assessment will be used throughout the course of the study to evaluate tolerability. Additionally, the actions that will be taken to evaluate safety will be the monitoring of adverse events, vital signs, and changes in concomitant medications. Digital photographs will be taken at each visit (excluding Visit 3).

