Safety Endpoints:	
Safety/tolerability endpoints are monitored by members of the study staff. They include the following:
 
 - Changes in local skin reaction - Changes in AEs and serious adverse events (SAEs) - Changes in vital signs and physical examinations - Changes in concomitant procedures/medications - Presence of signs/symptoms of irritation of the skin.
Statistical Methods:	
 - All analyses of the pooled individual patient data will be performed with the use of SPSS software using a two-way Chi-square test analysis, t-tests, odds ratios, and analysis of variance (ANOVA).
Assessments:	
 - Hand Eczema Severity Index 
 o Investigator-rated: clinical evaluation of both the extent and intensity of hand dermatitis 
 ▪ Clinical signs: erythema, infiltration/papulation, vesicles, figures, scaling, and edema ▪ Locations: fingertips, fingers (excluding tips), palms of hands, backs of hands, wrists ▪ Extent is graded on a visual 5-point scale ▪ Intensity is graded on a visual 4-point scale - Local Skin Reaction Assessment 
 o Investigator-rated: clinical grading score of erythema, induration/papulation, and lichenification 
 ▪ Each parameter is graded on a visual 4-point scale - Subject's Local Dermal Tolerability Assessment: 
 o Subject-Rated: clinical grading score of pruritus 
 ▪ Each parameter is graded on a visual 4-point scale - See assessments reference at end
Randomization:	
 - The subjects will be randomized to receive either the active or control medication based on a 3:1 randomization scheme - Out of 20 total subjects, 15 will receive the active treatment while 5 will receive the vehicle
Photography:	
 - Digital photographs will be taken at proximal and distal views of the dorsal as well as palmar surfaces of the hand

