6.4.2 Visit 2 (Day 0): Baseline

The subject will return to the clinic and will be queried for any changes in health status since the previous visit, including concomitant medications and therapies. A urine pregnancy test with negative result confirmed will be performed for all WOCBP. The Hand Eczema Severity Index and Investigator's Global Assessment will be completed. Baseline reading of local skin reactions will be assessed prior to IP application. The Subject's Local Dermal Tolerability Assessment will be performed. IP will be dispensed to the subject. IP will then be dispensed and subject will apply the first dose in clinic. The subject diary will be dispensed. Digital photographs will be taken at proximal and distal views of both the dorsal as well as palmar surfaces of the subject's hand (treatment area). The subject will be scheduled to return to clinic for Visit 3 in accordance with the treatment window.

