7.2.2 Sample Size

The total sample size needed is 20 subjects that are 12 years of age and older. Each subject will be randomized in a 3:1 ratio to receive either the active (15 subjects) or vehicle (5 subjects) product throughout the study. Endpoints will be evaluated using a 2-sided Chi-square test and t-test at the 0.05 significance level.

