7.2.8 Efficacy Analyses

Efficacy variables will be analyzed at the time points shown in the visit schedule.

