7.2.8.1 Primary Efficacy Analyses

This study is concerned with the efficacy of topical AFX 5931 in the treatment of mild to moderate hand dermatitis. Changes in clinical scores recorded via the Hand Eczema Severity Index and Investigator's Global Assessment will be the primary modes of efficacy evaluation.

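### Mean HECSI change is compared without adjusting for Visit 2 HECSI: valid, but usually less precise than it could be, and cheap to improve within stated limits

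*Combined protocol and SAP*

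**What the plan says.** Four places describe the analysis of means.

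- Section 7.2.1: "An analysis of means using an independent samples t-test and ANOVA will be used". The next sentence reads: "Primary analysis will be completed with the help of a chi-square analysis and assessment of relative risk and odds ratios".
- Section 7.2.2: "Endpoints will be evaluated using a 2-sided Chi-square test and t-test at the 0.05 significance level".
- The synopsis, under Statistical Methods, lists "two-way Chi-square test analysis, t-tests, odds ratios, and analysis of variance (ANOVA").
- Section 7.2.8.1 opens with "Changes in clinical scores recorded via the Hand Eczema Severity Index and" goes on to name the Investigator's Global Assessment (IGA), and makes these changes the main efficacy measures. Section 7.2.8 adds: "Efficacy variables will be analyzed at the time points shown in the visit schedule".

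No section names a covariate, a factor for the ANOVA, or any adjustment for baseline.

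The baseline value is collected. The synopsis (Study Design) says that "baseline readings of efficacy as well as safety/tolerability assessments will be obtained prior to application of the IP". The visit schedule in 6.3 marks HECSI at Visit 2, and 6.4.2 confirms it: "The Hand Eczema Severity Index and Investigator's Global Assessment will be completed. Baseline reading of local skin reactions" follows directly. Section 7.2.2 fixes the arms at 15 active and 5 vehicle.

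**The concern.** No single sentence says that mean HECSI change is compared by t-test. That follows from reading 7.2.1, 7.2.2 and 7.2.8.1 together; HECSI runs from 0 to 360, so it is the natural target for an analysis of means. On that reading, baseline enters only through the change score, which fixes its slope at 1 instead of estimating it.

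With 5 vehicle subjects the interval for the mean difference will be wide, and a chance baseline difference between arms is likely. A pre-treatment covariate that is already collected could narrow the interval. The ANOVA does not clearly supply this. If it is one-way by arm at one visit, it repeats the equal-variance t-test (F = t²). A repeated-measures ANOVA is also a possible reading.

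**Working it through.** **Inputs.** From 7.2.2: N = 20, split 15:5 (20 × 3/4 = 15, 20 × 1/4 = 5), two-sided 0.05. The plan states no power, effect size, SD or correlation, so N = 20 cannot be reproduced and everything below rests on assumptions. Assumed: normal scores, baseline SD 1, follow-up SD k, correlation r.

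**Variance ratio under a common slope.**

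- Change score, per subject: k² + 1 − 2rk.
- ANCOVA residual, per subject: k²(1 − r²).
- Cost of estimating the slope: 1 + 1/(N − 4) = 17/16 = 1.0625 at N = 20.
- Ratio, ANCOVA over change: (17/16) × k²(1 − r²) / (k² + 1 − 2rk).

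With k = 1 this is (17/16)(1 + r)/2. Half-widths are in baseline SDs, and power is for a difference of 1 baseline SD; both are shown as change / ANCOVA.

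| r | Ratio | 95% CI half-width | Power |
|---|---|---|---|
| 0.3 | 1.0625 × 0.65 = 0.69 | 1.27 / 1.05 | 34 / 46% |
| 0.5 | 1.0625 × 0.75 = 0.80 | 1.07 / 0.96 | 45 / 53–54% |
| 0.7 | 1.0625 × 0.85 = 0.90 | 0.83 / 0.79 | 66 / 70% |
| 0.9 | 1.0625 × 0.95 = 1.01 | 0.48 / 0.48 | 98 / 98% |

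Break-even is r = 32/17 − 1 = 0.88. Simulation at 15:5 agrees with the formula.

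**Other SD ratios, r = 0.5.**

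- k = 1.25: 1.0625 × 1.5625 × 0.75 / 1.3125 = 0.95.
- k = 1.5: 1.0625 × 2.25 × 0.75 / 1.75 = 1.02.
- k = 0.75: 0.55.

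Entry is restricted to IGA 2 or 3 (section 4.1) and follow-up is not, so k above 1 is plausible.

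**Worst case under a common slope.** Since k² + 1 − 2rk = k²(1 − r²) + (1 − rk)², the ratio cannot exceed the slope-estimation cost, and it reaches that cost when rk = 1. At N = 20 this is 1.0625. With 16 evaluable it is 1 + 1/12 = 1.083 (simulated at 12:4: about 1.08). The lost degree of freedom (17 instead of 18) adds roughly one percentage point to the squared interval width.

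**Chance imbalance.** The baseline difference D has SD √(1/15 + 1/5) = 0.516, so |D| exceeds 0.5 SD in 33% of trials. Under a common slope the change contrast shifts by −(1 − rk)D, which is zero at rk = 1 and reverses beyond it; ANCOVA has no shift. In null trials with |D| above 0.5 SD and k = 1, the change test rejects in about 10, 8.5, 7 and 6% at the four r values. This is offset by about 2.5, 3, 4 and 4.6% in the remaining trials. Overall both tests reject in about 5%.

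**Unequal slopes.** Take k = 1 with r = 0.3 in active and 0.9 in vehicle. Given D, the arm means move by +0.25D and −0.75D.

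- Change shift: (0.3 − 1)(0.25) + (0.9 − 1)(0.75) = −0.25 per unit of D.
- ANCOVA: the pooled slope is about (14 × 0.3 + 4 × 0.9)/18 = 0.433, so the shift is 0.3 × 0.25 + 0.9 × 0.75 − 0.433 = +0.32.
- Simulated variance ratio: 1.18, or 0.84 with the two correlations exchanged between arms. A more extreme pair (0.2 and 0.95) gives 1.33.

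**Unequal variances.** Let active have follow-up SD 0.5 and vehicle 1, with r = 0.7 in both. Change variances are 0.25 + 1 − 0.7 = 0.55 and 1 + 1 − 1.4 = 0.60. Residual variances are 0.25 × 0.51 = 0.1275 and 0.51, a fourfold difference; the slopes also differ (0.35 and 0.70). With no mean difference, ANCOVA rejects in about 16% and the pooled change test in about 5%. Separately, at r = 0.5 with vehicle residual SD twice active, 95% interval coverage is 85% for ANCOVA, 86% for pooled change and 94% for Welch.

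**The case against.** The strongest reply is that nothing here is wrong. The unadjusted test on change is valid under randomization. The target is inferred, the plan ties its primary analysis to chi-square, and in a 20-subject pilot without a power statement the choice between ANCOVA and change score is largely the analyst's. All of that stands, and it limits the point to an optional gain in precision.

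The reply also has force on size. The gain at r = 0.5 nearly vanishes, or becomes a small loss, if the follow-up SD is larger than baseline. The 6% ceiling needs 20 evaluable subjects and a common slope, whereas withdrawn patients are not replaced (4.3) and missing values stay blank (7.2.4). If active treatment compresses the scores, slopes and residual variances may well differ between arms, and ANCOVA can then be less robust than the test it replaces. These limits are built into the verdict and are the reason for the Welch test.

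A reader might infer that the plan ignores baseline, that its test is biased, or that the primary analysis is unadjusted where it should be adjusted. The documents support none of these: change already uses baseline, overall type I error is about 5% when the arms have equal variances, and 7.2.1 names chi-square for the primary analysis.

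**Conclusion.** This is a cheap improvement, not an error. Read together, the sections leave mean HECSI change compared without covariate adjustment, and for r up to about 0.88 with equal SDs this gives up precision. At r = 0.5 the loss is about 20% of the variance, or a half-width of 1.07 instead of 0.96 SD. The figures rest on assumed r and SDs, 20 evaluable subjects and a common slope.

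The advantage is not universal. At r = 0.5 it is about 5% at an SD ratio of 1.25 and turns into a loss of about 2% at 1.5. The cost is bounded near 6% only under a common slope with all 20 subjects, near 8% with 16. It was about 20% where slopes differed strongly, and that is an example, not a ceiling.

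A reader might infer that ANCOVA always removes the effect of baseline imbalance. It does so only under a common slope; otherwise the shift can be larger and reversed. Nor does it protect against unequal arm variances.

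**What to change.** In 7.2.1, keep the sentence on means for the other scores, so that IGA does not lose its stated analysis, and add:

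> For HECSI, change from baseline at each scheduled follow-up visit will be compared between arms by ANCOVA with treatment as factor and Visit 2 HECSI as covariate, reporting the adjusted mean difference and 95% CI; a Welch t-test on change will be reported alongside it because ANCOVA assumes equal residual variances and a common slope.

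Make matching edits in 7.2.2 and in the synopsis under Statistical Methods. The wording does not choose a main time point, which is a separate decision. The Welch test addresses unequal variances but is not baseline-adjusted; the plan should say so.

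The cost is text in three places. ANCOVA uses the same two HECSI values per subject as the change score, so no visit, measurement or subject is added or lost. The statistical price is one residual degree of freedom, a small variance loss when r times the SD ratio is near 1, and sensitivity to unequal slopes or variances.

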9.0 Research Study Assessments

Primary Endpoint Evaluations

Hand Eczema Severity Index:

Clinical Signs	Fingertips	Fingers (except tips)	Palms of Hands	Backs of Hands	Wrists
Erythema (E)					
Infiltration (I)					
Vesicles (V)					
Fissures (F)					
Scaling (S)					
Oedema (O)					
SUM					
Extent					
Total HECSI Score = _____	SUM * Extent	SUM * Extent	SUM * Extent	SUM * Extent	SUM * Extent

Reference: Held et al – British Journal of Dermatology – Volume 152 Issue 2 (2005) pages 302-307

Each hand is divided into five areas [fingertips, fingers (except the tips), palms, back of hands and wrists]. The clinical signs of erythema, induration/papulation, vesicles, fissuring, scaling and oedema are graded on the following scale:

0 = no skin changes

1 = mild disease

2 = moderate

3 = severe

Per each location (combining both hands), the affected region was given a score for extent of surface area involvement on the following scale:

0 = 0%;

1 = 1–25%

2 = 26–50%

3 = 51–75%

4 = 76–100%

Finally, the score given for the extent at each location was multiplied by the sum of the intensity of clinical features. The total sum (HECSI score, highlighted above) was calculated, ranging from 0 to a maximum severity score of 360.

Investigator's Global Assessment:

The investigator will rate the subject's hand dermatitis on a visual 5-point scale as follows:

0: Clear:	No signs of HE
1: Almost clear:	Just perceptible scaling and/or erythema;
2: Mild disease:	Mild scaling and/or mild erythema, and/or mild cracking
3: Moderate disease:	Moderate scaling and/or erythema, and/or moderate cracking/fissuring
4: Severe disease:	Severe scaling and/or severe erythema, and/or severe cracking/fissuring

Dorsal and palmar surfaces of the hand are evaluated *together*.

Reference: Diamant et al. - Dermatology Basel - Volume 207, Issue 1 (2003) pages 37-42

Secondary Endpoint Evaluations

Subject's Local Dermal Tolerability Assessment:

The subjects will be asked to grade their feeling of itching at the application site using a 4-point tolerability scale, where 0=None, 1=Mild, 2=Moderate, and 3=Severe.

Puritus: Definition: itching

0 = None:	No itching
1 = Mild:	Occasional, slight itching/scratching
2 = Moderate:	Constant or intermittent itching/scratching/discomfort that is not disturbing sleep
3 = Severe:	Bothersome itching/scratching/discomfort that is disturbing sleep

Local Skin Reaction Assessment:

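### The method named for the primary analysis needs a binary outcome, but the primary measures are HECSI and IGA score changes and neither is assigned a test; cutting HECSI at 15 v 5 would cost power

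*Combined protocol and SAP*

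**What the plan says.** Section 7.2.8.1 defines primary efficacy through score changes: "Changes in clinical scores recorded via the Hand Eczema Severity Index and Investigator's Global Assessment will be the primary modes of efficacy evaluation". Section 9.0 shows that both scores are graded. For HECSI, "The total sum (HECSI score, highlighted above) was calculated, ranging from 0 to a maximum severity score of 360"; IGA is an ordered scale with five levels, 0 to 4.

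Section 7.2.1 ties one method to the primary analysis: "Primary analysis will be completed with the help of a chi-square analysis and assessment of relative risk and odds ratios". It also plans interval estimates for a binary result: "Ninety-five percent confidence intervals will be constructed for proportions of successes". Directly before the chi-square sentence it says: "An analysis of means using an independent samples t-test and ANOVA will be used". Section 7.2.2 gives both tests without ranking them: "Endpoints will be evaluated using a 2-sided Chi-square test and t-test at the 0.05 significance level". The synopsis lists chi-square, t-tests, odds ratios and ANOVA, again unranked.

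The plan does not define success on either scale, give a cut-off, or say which test belongs to which measure. It states no effect size, SD, expected response rate or target power.

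**The concern.** The method named for the primary analysis and the measures named as primary do not fit together unless the scores are first cut in two. Cutting a 0-360 score discards most of its information, and with 5 vehicle subjects little is left. By enumeration of the 15 v 5 tables, an uncorrected chi-square result in favour of active needs at least:

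- 8/15 active successes if vehicle has 0/5
- 11/15 if vehicle has 1/5
- 13/15 if vehicle has 2/5
- 15/15 if vehicle has 3/5

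A substantial true improvement in HECSI could therefore be reported as a non-significant primary result although the scores collected would have shown it. Because no test is assigned to a measure, the choice of which result leads the report is also left open until the data are seen.

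**Working it through.** **Inputs from the plan.** Allocation is in 7.2.2: "Each subject will be randomized in a 3:1 ratio to receive either the active (15 subjects) or vehicle (5 subjects) product throughout the study". Level and sidedness are in 7.2.1: "The analysis will be 2-sided and conducted at the 0.05 significance level".

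**Assumed inputs, because the plan gives none.** Normally distributed HECSI change, equal SDs, standardised difference d from 1.0 to 2.0, vehicle success of 10% to 50% at the cut, no dropout.

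**The plan's own figure.** N = 20 has no stated derivation and cannot be reproduced. Working backwards, the pooled t-test at 15 v 5 reaches 80% power only at d of about 1.53.

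**Pooled t-test.** Noncentral t with 15 + 5 − 2 = 18 df and noncentrality d × √(15 × 5 / 20) = 1.936 d.

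**Chi-square on a cut score.** Active success rate p1 = Φ(Φ⁻¹(p0) + d), where p0 is the vehicle rate. For example, p0 = 0.10 and d = 1.0 give Φ(−1.282 + 1.0) = 0.389. Power is the summed probability of the significant tables among all 16 × 6 possible tables, using the uncorrected Pearson statistic.

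**Results (%).** Ranges are over p0 = 10, 20, 30, 40 and 50%. Losses were taken before rounding.

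| d | Pooled t | Chi-square | Loss (points) |
|---|---|---|---|
| 1.0 | 45.0 | 11.4 to 38.3 | 6.7 to 33.6 |
| 1.2 | 59.4 | 24.7 to 50.1 | 9.4 to 34.7 |
| 1.5 | 78.4 | 50.8 to 67.3 | 11.1 to 27.6 |
| 2.0 | 95.5 | 72.0 to 88.0 | 7.6 to 23.5 |

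The overall loss is 6.7 to 34.7 points. At d = 0.8 it is about 3 to 27. The uncorrected Pearson test is the comparison kindest to the plan: against Fisher's exact test the pooled t-test gains 17 to 47 points for d from 1.0 to 2.0. Part of the loss at low vehicle rates arises because the Pearson test is conservative there (actual size 2.2% at p0 = 10%, 5.2% at p0 = 50%).

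**Is the pooled t-test a safe replacement?** Not at 15 v 5. In simulation with no effect it rejects about 11% of the time when the vehicle SD is 1.5 times the active SD, and about 16% at 2 times. Welch's form holds about 5.5%. With equal SDs its power is about 39, 52, 70 and 90% at d = 1.0, 1.2, 1.5 and 2.0, which is 6 to 9 points below the pooled test. It stays above the top of the chi-square range at each d, though narrowly at the most favourable cut. At d = 1.0 the gain runs from 39 − 38 = 1 point to 39 − 11 = 28 points.

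**IGA.** Five ordered categories were simulated from a normal latent score with cuts 0.9 SD apart. For d from 1.0 to 2.0 and vehicle success of 10-30%, a rank-sum test gains about 2 to 26 points over a 2×2 chi-square (IGA 0 or 1 v 2 to 4). If the chi-square were instead run on the 2×5 table, it would ignore the order of the grades, and the rank-sum gain is about 6 to 25 points. These figures depend on the assumed spacing.

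**The case against.** A reader might infer that the plan dichotomises HECSI and puts the t-test second. The documents do not support that as fact. No section says that HECSI is cut, gives a cut-off, or assigns chi-square to HECSI. The t-test sentence comes before the chi-square sentence in 7.2.1 and is nowhere called secondary, and 7.2.2 lists the two side by side. The wording of the primary sentence does not exclude other tests. Chi-square for an IGA response and the t-test for HECSI is a possible joint reading, and under it the HECSI loss is zero. This stands, so the power figure must be conditional. It does not remove the point: that reading is not written anywhere either, chi-square is the only method tied to the primary analysis, and IGA would still be cut.

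It is also fair that this is a 20-subject pilot with no power target, that even the pooled t-test has only 45% power at d = 1.0, and that means and SDs by arm will be reported in any case. The score information is thus lost from the primary test, not from the report. But the plan does test at the 0.05 level, and a mean difference with an interval serves an objective of measuring efficacy better than a 2×2 table with 5 controls.

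Finally, HECSI change may be skewed and the SDs may differ. That stands against a bare pooled t-test and is why the fix uses Welch's form with a rank-based check.

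**Conclusion.** The mismatch is established from the text: a binary-outcome method is named for the primary analysis of two graded score changes, and no test is assigned to either measure. The size is conditional. If HECSI is cut, the uncorrected chi-square loses about 7 to 35 points of power against the pooled t-test for d of 1.0 to 2.0, assuming a normal score, equal SDs and 10-50% vehicle success. Against Welch's test, the safer choice here, the loss is about 1 to 28 points under the same assumptions. If HECSI is already meant for the t-test, the HECSI loss disappears and the point reduces to IGA and to stating the assignment. The documents do not settle which reading is intended.

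**What to change.** In 7.2.1 and 7.2.2, assign a test to each measure:

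- **HECSI:** the primary analysis is the between-arm difference in mean change from Visit 2 to Visit 4 with a 95% confidence interval, using the unequal-variance (Welch) form of the independent-samples t-test already planned. Add an exact rank-sum p-value as a check for skew.
- **IGA:** compare the arms on the full 0-4 scale with an exact Wilcoxon rank-sum test.
- Keep both measures as the primary efficacy evaluation, as 7.2.8.1 has them.
- Report success proportions, relative risks and odds ratios as supportive.

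This needs no new data, visits or subjects. It does require the sponsor to commit to Visit 4 as the primary time point, since 7.2.8 refers only to the scheduled visits. There are two small downsides: a mean score difference is less direct to read than a success rate, and Welch's test gives up about 6 to 9 points of power to the pooled test if the SDs are in fact equal.
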